##### **4.4.3.2 BI score associated with abutment teeth at Week 6 and Week 12**

The BI scoring system is described in [Section 4.4.1.1](#). The BI score associated with abutment teeth will be calculated as the average index value associated with abutment teeth only.

##### **4.4.3.3 Number of bleeding sites associated with abutment teeth at Week 6 and Week 12**

The number of bleeding sites associated with abutment teeth is the number of sites with a BI value of 1 or 2, associated with abutment teeth only.

##### **4.4.3.4 MGI score associated with abutment teeth at Week 6 and Week 12**

The MGI scoring system is described in [Section 4.4.2.2](#). The MGI score associated with abutment teeth will be calculated as the average index value associated with abutment teeth only.

#### **4.4.3.5 Overall TPI score associated with abutment teeth at Week 6 and Week 12**

The TPI scoring system is described in [Section 4.4.2.3](#). The Overall TPI score associated with abutment teeth will be calculated as the average index value over sites associated with abutment teeth only.

#### **4.4.3.6 Interproximal TPI score associated with abutment teeth at Week 6 and Week 12**

The TPI scoring system is described in [Section 4.4.2.3](#). The Interproximal TPI score associated with abutment teeth will be calculated as the average index value over interproximal sites (distal and mesial) associated with abutment teeth only.

#### **4.4.3.7 CI score associated with abutment teeth at Week 6 and Week 12**

The CI scoring system is described in [Section 4.4.2.6](#). The CI score associated with abutment teeth will be calculated as the average index value associated with abutment teeth only.

#### **4.4.3.8 ODI score associated with abutment teeth at Week 6 and Week 12**

The ODI scoring system is described in [Section 4.4.2.7](#). The ODI score associated with abutment teeth will be calculated as the average index value associated with abutment teeth only.

#### **4.4.3.9 OHI score associated with abutment teeth at Week 6 and Week 12**

The OHI score associated with abutment teeth is a composite score of the CI and the ODI calculated as the sum of the mean CI score and the mean ODI score associated with abutment teeth only.

### **4.4.4 Handling of Missing Values/Censoring/Discontinuations**

Missing data will not be replaced or imputed. Subjects who withdraw from the study prematurely will be included in the statistical analyses up to the point of discontinuation.

Also, missing due to COVID-19 will be assessed separately at BDRM and necessary actions will be taken on analysis for primary and key secondary endpoints (see section 4 for more details).

## **4.5 Analysis of Secondary and Exploratory Objectives**

### **4.5.1 Efficacy (Secondary)**

Each secondary variable will be analyzed separately as per the primary variable ([Section 4.4.1.2](#)). All analyses will be conducted on the mITT population only. For all of the secondary analyses, normality assumptions in ANCOVA models will be checked and accounted for in the same way as for the primary variable.

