## 2.1 Study Rationale

This clinical study is the first known design to explicitly investigate the efficacy and safety of the use of a range of dental/denture products on the maintenance of oral health. The endpoints utilized in this study have been chosen as markers of general oral health of subjects who wear removable partial dentures. This study is required to evaluate whether potential claims associated with the use of the range of dental/denture products are valid as well as to inform the dental practitioner on the potential benefits to oral health of the range of dental/denture products.

Property of GSK Consumer Healthcare - Confidential

May not be used, divulged, published or otherwise disclosed without the consent of GSKCH

SP1963/SOP-208661: Template Version: 14 Mar 2019

Whilst the product range itself has not been previously clinically tested, the toothpaste and denture cleanser foam have been tested as individual products (or products very similar to those being tested) in a number of clinical studies (see [Background Section 2.2](#)). These studies demonstrate the efficacy and safety of the individual study products. Additionally, the experimental dentifrice and mouthrinse are also very similar to existing marketed products that have an acceptable risk-benefit ratio. In conclusion, therefore, the benefits outweigh the risks identified for the intended use of the products comprising the interventional range of products.

Complete information for the products used in this range of dental/denture products may be found in the single reference safety document (SRSD), which for this study is the safety statement.

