| To capture photographic images of RPDs for each of the scores in the PDCI scale to assist study site staff with consistent evaluation of the PDCI over the duration of the study, to assist with future studies that might use this scale, and to aid to interpretation of results (including publication of the study outcomes). | Photographs of RPDs.                             |
| Safety   |  |
| To assess the safety and tolerability of a range of dental/denture products when used twice daily for 12 weeks.   | Treatment emergent adverse events and incidents. |

This study will be considered successful if a statistically significant improvement in BI, compared to the no intervention group (existing oral hygiene) at an alpha level of 0.05, is observed following 12 weeks twice daily use of a range of dental/denture products.

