### **12.2.6 Secondary Analyses**

The mITT population will be used for all secondary analyses. For all of the secondary analyses, Normality assumptions in ANCOVA models will be checked and accounted for in the same way as for the primary variable.

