#### 4.4.1.2 Statistical Hypothesis, Model, and Method of Analysis

The primary analysis is a comparison of the BI score between the Intervention Group and No Intervention Group at Week 12 for subjects eligible for the mITT population.

The null and alternative hypotheses to be tested in the primary analyses are:

$H_0$ : There is no treatment difference in mean BI score after 12 weeks

$H_1$ : There is a treatment difference in mean BI score after 12 weeks

An Analysis of Covariance (ANCOVA) model will be used for the primary analysis with treatment group, gender, denture material type (acrylic or cobalt chrome), and baseline mean overall MGI score (low, high) as factors and the baseline BI score as a covariate. The adjusted means and standard errors (SEs) of the two treatment groups together with the treatment difference, SE, 95% confidence interval of the difference, between-group p-value and the proportionate reduction will be provided in [Table 14.2.2.1.2](#) for the mITT population.

The proportionate reduction will be calculated as:

- Proportionate reduction =  $[(\text{Adjusted Mean of No Intervention Group} - \text{Adjusted Mean of Intervention Group}) / \text{Adjusted Mean of No Intervention Group}] * 100$ .

The assumption of normality and homogeneity of variance in the ANCOVA model will be investigated and if violated, data transformations will be investigated. If suitable transformations cannot be found, non-parametric tests will be performed, and results will be compared with the ANCOVA results. If the inferences from the two analyses are similar, then both sets of results will be reported and emphasis will be made on the ANCOVA results. In case of discrepancies between inferences of the ANCOVA and non-parametric analysis, results will be drawn from the non-parametric analysis.

Descriptive statistics (n, mean, SD, SE, median, minimum, maximum) of the primary variable will be provided at Baseline, Week 6 and Week 12 visits by treatment group (and overall for Baseline only) for the mITT population ([Table 14.2.2.1.1](#)).

The raw mean and SE of the BI score (whole mouth and associated with abutment teeth) will be presented graphically over time for each treatment group in [Figure 14.2.1.1](#) (mITT population).

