#### **4.5.1.1 Number of Bleeding Sites at Week 6 and Week 12**

At each post-baseline visit, the average number of bleeding sites will be analyzed using an ANCOVA model with treatment group, gender, denture material type (acrylic or cobalt chrome), and baseline mean overall MGI score (low, high) as factors and the baseline number of bleeding sites as a covariate. The adjusted means and SEs of the two treatment groups together with the treatment difference, SE, 95% confidence interval of the difference, between-group p-value and the proportionate reduction will be provided in [Table 14.2.3.1.2](#) for the mITT population.

The proportionate reduction will be calculated as:

- Proportionate reduction =  $[(\text{Adjusted Mean of No Intervention Group} - \text{Adjusted Mean of Intervention Group}) / \text{Adjusted Mean of No Intervention Group}] * 100$ .

Descriptive statistics (n, mean, SD, SE, median, minimum, maximum) of the number of bleeding sites will be provided at Baseline, Week 6 and Week 12 visits by treatment group (and overall for Baseline only) for the mITT population ([Table 14.2.3.1.1](#)).

The raw mean and SE of the number of bleeding sites (whole mouth and associated with abutment teeth) will be presented graphically over time for each treatment group in [Figure 14.2.2](#) (mITT population).

The number of bleeding sites will be listed by subject and visit in [Listing 16.2.6.6.1](#) for all randomized subjects.

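### Seventeen secondary comparisons have unadjusted p-values and no gate, order or nominal label, and the key secondary endpoints are never named

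*SAP*

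**What the plan says.** **Primary.** The Protocol's success statement after Table 3-1 rests on BI alone, "compared to the no intervention group (existing oral hygiene) at an alpha level of 0.05". Hypotheses are written only for BI at Week 12. The alternative has no direction ("There is a treatment difference in mean BI score after 12 weeks", SAP 4.4.1.2), so the test is two-sided. No interim analysis is planned.

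**Secondary.** Protocol 12.2.6 fixes the population ("The mITT population will be used for all secondary analyses"), and SAP 4.5.1 gives the rule: "Each secondary variable will be analyzed separately as per the primary variable". The visits are modelled separately. For bleeding sites, for example, SAP 4.5.1.1 says "At each post-baseline visit, the average number of bleeding sites will be analyzed using an ANCOVA model". Each comparison produces a treatment difference, a 95% confidence interval and a between-group p-value. The MGI model differs slightly: it omits the MGI stratum because baseline MGI is already the covariate.

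**Status of the secondaries.** The readable text has no alpha for the secondaries, no testing order, no condition on the primary and no statement that their p-values are nominal. The SAP's table of changes from the protocol adds none. SAP 4.4.4 provides that, for data missing because of COVID-19, "necessary actions will be taken on analysis for primary and key secondary endpoints", but no secondary is designated as key.

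**Purpose.** Protocol 2.1: "This study is required to evaluate whether potential claims associated with the use of the range of dental/denture products are valid".

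**The concern.** BI at Week 12 measures bleeding only. A claim about plaque, calculus, debris, overall oral hygiene or denture cleanliness would have to come from a secondary test. The plan does not say which of the 17 may support a conclusion, or whether any may do so if BI fails. The abutment-tooth and questionnaire endpoints are labelled exploratory; the secondaries carry no comparable limit, and each has its own efficacy objective in Table 3-1.

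The tests also overlap. OHI is the sum of CI and ODI, the bleeding-site count is derived from the BI scores, and interproximal TPI uses a subset of the overall TPI sites. One chance imbalance could therefore appear as two or three findings that seem to support each other.

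The undefined key secondary set adds a practical problem. The decision on COVID-related missing data is to be taken at the blind data review meeting, for endpoints that no one has listed.

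**Working it through.** **1. The plan's own figure.** One primary test and no interim look give a type I error of 0.05, as stated. The secondaries do not change it.

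**2. Count of secondary tests** (Protocol summary, Table 3-1 and 12.2.6; SAP 4.5.1.1 to 4.5.1.9).

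- Bleeding sites, MGI, overall TPI, interproximal TPI, PDCI, CI, ODI and OHI, each at Weeks 6 and 12: 8 × 2 = 16
- BI at Week 6: 1
- Total: 17

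**3. Level per test.** None is stated for the secondaries. An unadjusted 95% interval and p-value for each imply two-sided 0.05, or 0.025 in the direction favouring the products.

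**4. Expected number of false results if no secondary has a true effect.** This does not depend on correlation.

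- Either direction: 17 × 0.05 = 0.85
- Favouring the products: 17 × 0.025 = 0.425

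**5. Chance of at least one, independent tests.**

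- Either direction: 1 − 0.95^17 = 0.582
- Favouring the products: 1 − 0.975^17 = 0.350

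**6. Chance of at least one, correlated tests.** With a common correlation ρ and c = 1.96, the favourable-direction rate is

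1 − ∫ Φ((c − √ρ·w)/√(1−ρ))^17 φ(w) dw.

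For either direction, Φ(·) is replaced by the probability of lying between −c and c given w. The documents give no correlation, so ρ is an assumption:

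| ρ | Favouring the products | Either direction |
|---|---|---|
| 0 | 0.350 | 0.582 |
| 0.3 | 0.254 | 0.493 |
| 0.5 | 0.194 | 0.386 |
| 0.7 | 0.135 | 0.271 |
| 0.9 | 0.074 | 0.149 |

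**7. Simulation with the overlap built in.** OHI was set to CI + ODI. BI with bleeding sites, and overall with interproximal TPI, were correlated 0.90 to 0.97. Week 6 with Week 12 was correlated 0.4 to 0.8, and other pairs mostly 0.1 to 0.75. The rate was 16–26% favouring the products and 32–48% in either direction.

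**8. What a gate does.** In a simulation with correlation 0.5 between most endpoints, 0.95 for the two overlapping pairs, and 0.5 or 0.7 between visits, 15–17% of trials had a false favourable secondary without a significant favourable BI at Week 12. A gate removes these. Across the step 7 settings, the chance that the primary and at least one secondary are both significant, in either direction, was 4.0–4.7% when nothing works. A gate alone does not protect the secondaries once the primary effect is real. For that, a fixed sequence or a Holm step after the gate is needed.

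**The case against.** The strongest reply is that secondaries are supportive by convention, and parts of the plan fit that reading. Success is tied to BI alone, hypotheses are written only for BI, and the per-protocol analysis is limited to BI. Some documented prior evidence also points to true effects. Protocol 2.2 reports clinical evidence that the foam removes denture plaque, and says very similar dentifrice formulations have been evaluated for gingivitis. The global null is therefore a worst-case convention.

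These points stand, and they rule out two stronger readings.

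- A reader might infer that any secondary p-value below 0.05 has the same standing as the primary, even if BI fails. The documents do not say so. The sentence in SAP 4.5.1 refers back to the model section and prescribes method; SAP 4.5.2 uses similar wording for the exploratory endpoints. The defect is silence about status.
- A reader might infer a false-claim rate of 35–40% where 5% was promised. The 39% at ρ = 0.5 counts results in either direction, and a result favouring no intervention cannot support a product claim. It also depends on an assumed correlation. The documents attach 0.05 only to the primary.

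The link to claims is also partly inference. Protocol 2.1 speaks of claims for the range in general, and of informing practitioners, without naming secondary endpoints.

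The reply does not supply the missing statement. Neither document calls the secondaries supportive, and BI cannot cover the non-bleeding objectives.

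**Conclusion.** The gap is real and should be closed, although the primary inference is sound. Seventeen unadjusted comparisons have no stated inferential status, and the key secondary set is undefined.

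If no secondary has a true effect, the chance of at least one false result favouring the products is about 19% at an assumed common correlation of 0.5. It ranges from 7% at 0.9 to 35% under independence, against 2.5% for a single test. In either direction it is about 39% (15% to 58%). Even at correlation 0.9 the rate is about three times that of one test. If some secondary effects are real, fewer comparisons can give a false positive and the rates fall. The count of 17 and the missing status statement depend on no assumption about correlation.

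**What to change.** Amend SAP 4.5.1 and Protocol 12.2.6 before database lock and unblinding; an order chosen after results are seen controls nothing. The text should state:

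- Secondary hypotheses are tested confirmatorily only if BI at Week 12 is significant at two-sided 0.05.
- They are then tested at two-sided 0.05 in a short fixed sequence of Week 12 endpoints, stopping at the first p ≥ 0.05. The sponsor should choose the sequence. One example is number of bleeding sites, MGI, overall TPI, PDCI. This is a selection from Table 3-1, which lists more endpoints.
- That list defines the key secondary endpoints in SAP 4.4.4.
- All other secondary comparisons, including all Week 6 results and anything after the stop, are reported with nominal p-values.

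If no hierarchy is wanted, the minimum is one sentence stating that all 17 secondary p-values are nominal, unadjusted and supportive only. The key secondary endpoints in SAP 4.4.4 would then still need to be named, or the term removed.

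The cost is one paragraph and some table footnotes. No new data, subjects or models are needed, and the primary keeps its full alpha. The downside is that secondaries outside the sequence, or after the stop, cannot be called demonstrated.

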#### **4.5.1.1 Number of Bleeding Sites at Week 6 and Week 12**

At each post-baseline visit, the average number of bleeding sites will be analyzed using an ANCOVA model with treatment group, gender, denture material type (acrylic or cobalt chrome), and baseline mean overall MGI score (low, high) as factors and the baseline number of bleeding sites as a covariate. The adjusted means and SEs of the two treatment groups together with the treatment difference, SE, 95% confidence interval of the difference, between-group p-value and the proportionate reduction will be provided in [Table 14.2.3.1.2](#) for the mITT population.

The proportionate reduction will be calculated as:

- Proportionate reduction =  $[(\text{Adjusted Mean of No Intervention Group} - \text{Adjusted Mean of Intervention Group}) / \text{Adjusted Mean of No Intervention Group}] * 100$ .

Descriptive statistics (n, mean, SD, SE, median, minimum, maximum) of the number of bleeding sites will be provided at Baseline, Week 6 and Week 12 visits by treatment group (and overall for Baseline only) for the mITT population ([Table 14.2.3.1.1](#)).

The raw mean and SE of the number of bleeding sites (whole mouth and associated with abutment teeth) will be presented graphically over time for each treatment group in [Figure 14.2.2](#) (mITT population).

The number of bleeding sites will be listed by subject and visit in [Listing 16.2.6.6.1](#) for all randomized subjects.

#### **4.5.1.2 MGI Score at Week 6 and Week 12**

At each post-baseline visit, the MGI score will be analyzed using an ANCOVA model with treatment group, gender and denture material type (acrylic or cobalt chrome) factors and the baseline MGI score as a covariate. For the analysis of MGI the stratification factor of MGI will not be included as the baseline value of MGI is included as a covariate. The adjusted means and SEs of the two treatment groups together with the treatment difference, SE, 95% confidence interval of the difference, between-group p-value and the proportionate reduction will be provided in [Table 14.2.4.1.2](#) for the mITT population.

The proportionate reduction will be calculated as:

- Proportionate reduction =  $[(\text{Adjusted Mean of No Intervention Group} - \text{Adjusted Mean of Intervention Group}) / \text{Adjusted Mean of No Intervention Group}] * 100$ .

Descriptive statistics (n, mean, SD, SE, median, minimum, maximum) of the MGI score will be provided at Baseline, Week 6 and Week 12 visits by treatment group (and overall for Baseline only) for the mITT population ([Table 14.2.4.1.1](#)).

The raw mean and SE of the MGI score (whole mouth and associated with abutment teeth) will be presented graphically over time for each treatment group in [Figure 14.2.3](#) (mITT population).

The MGI value obtained for each tooth, surface and site will be listed by subject and visit in [Listing 16.2.6.2](#) for all randomized subjects. The MGI score will be listed by subject and visit in [Listing 16.2.6.6.1](#) for all randomized subjects.

#### **4.5.1.3 Overall TPI Score at Week 6 and Week 12**

At each post-baseline visit, the Overall TPI score will be analyzed using an ANCOVA model with treatment group, gender, denture material type (acrylic or cobalt chrome), and baseline mean overall MGI score (low, high) as factors and the baseline Overall TPI score as a covariate. The adjusted means and SEs of the two treatment groups together with the treatment difference, SE, 95% confidence interval of the difference and between-group p-value will be provided in [Table 14.2.5.1.2](#) for the mITT population.

Descriptive statistics (n, mean, SD, SE, median, minimum, maximum) of the Overall TPI score will be provided at Baseline, Week 6 and Week 12 visits by treatment group (and overall for Baseline only) for the mITT population ([Table 14.2.5.1.1](#)).

The raw mean and SE of the Overall TPI score (whole mouth and associated with abutment teeth) will be presented graphically over time for each treatment group in [Figure 14.2.4](#) (mITT population).

The TPI value obtained for each tooth, surface and site will be listed by subject and visit in [Listing 16.2.6.3](#) for all randomized subjects. The Overall TPI score will be listed by subject and visit in [Listing 16.2.6.6.1](#) for all randomized subjects.

#### **4.5.1.4 Interproximal TPI Score at Week 6 and Week 12**

At each post-baseline visit, the Interproximal TPI score will be analyzed using an ANCOVA model with treatment group, gender, denture material type (acrylic or cobalt chrome), and baseline mean overall MGI score (low, high) as factors and the baseline Interproximal TPI score as a covariate. The adjusted means and SEs of the two treatment groups together with the treatment difference, SE, 95% confidence interval of the difference and between-group p-value will be provided in [Table 14.2.6.1.2](#) for the mITT population.

Descriptive statistics (n, mean, SD, SE, median, minimum, maximum) of the Interproximal TPI score will be provided at Baseline, Week 6 and Week 12 visits by treatment group for (and overall for Baseline only) the mITT population ([Table 14.2.6.1.1](#)).

The Interproximal TPI score will be listed by subject and visit in [Listing 16.2.6.6.1](#) for all randomized subjects.

#### **4.5.1.5 Bleeding Index at Week 6**

The mean BI score at Week 6 will be analyzed and presented in the same way as stated in [Section 4.4.1.2](#) for the primary analysis.

#### **4.5.1.6 PDCI score at Week 6 and Week 12**

At each post-baseline visit, the PDCI score will be analyzed using an ANCOVA model with treatment group, gender, denture material type (acrylic or cobalt chrome), and baseline mean overall MGI score (low, high) as factors and the baseline PDCI score as a covariate. The adjusted means and SEs of the two treatment groups together with the treatment difference, SE, 95% confidence interval of the difference and between-group p-value will be provided in [Table 14.2.7.1.2](#) for the mITT population.

Descriptive statistics (n, mean, SD, SE, median, minimum, maximum) of the PDCI score will be provided at Baseline, Week 6 and Week 12 visits by treatment group (and overall for Baseline only) for the mITT population ([Table 14.2.7.1.1](#)).

The raw mean and SE of the PDCI score will be presented graphically over time for each treatment group in [Figure 14.2.5](#) (mITT population).

The PDCI score will be listed by subject and visit in [Listing 16.2.6.4](#) for all randomized subjects.

